29.2 Post hoc analyses

Any post-hoc exploratory analyses not identified in this SAP will be clearly identified as unplanned analyses. If unexpected missing data patterns are found in the data, we may conduct sensitivity analyses in addition to those predefined in this SAP.

30 Safety

An adverse event is an untoward medical occurrence after the administration of the first dose of a study drug through day 12 (± 2). The number of non-serious and serious adverse events, and the proportion of subjects reporting ≥ 1 adverse event, will be summarized by treatment group and severity (mild / moderate / severe). We will also report the number and reasons for treatment discontinuation because of a treatment-related adverse event, as judged by the principal investigator. AEs will be summarized by frequencies and percentages and analyzed with chi-square tests.

31 Statistical software

Data manipulation, tables, figures, listings and analyses will be performed and documented using R, Stata and IBM-SPSS software.

32 Statistical summaries

For tables, sample sizes for each treatment group will be presented as totals in the column header (N=xxx), where appropriate. Sample sizes shown with summary statistics are the number (n) of patients with non-missing values. Summaries for categorical variables will include only categories that patients had a response in. Percentages corresponding to null categories (cells) will be suppressed. Summaries for continuous variables will include mean and SD. Other summaries (e.g. median, quartiles or range) will be used as appropriate. Percentages will be rounded and reported to a single decimal place. Summaries that include p-values will report the p-value to three decimal places with a leading zero (0.001). P-values <0.001 will be reported as <0.001.

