## **6 STUDY PROCEDURES**

### **6.1 FLOW CHART**

Table 1. Trial flow chart

	Baseline	Start of treatment			Halfway follow-up		End of treatment	Final study visit	Withdrawal
Day	0	1	2	3-4	5 ( $\pm 1$ )	6-9	10	12 ( $\pm 2$ )	within 7 days after withdrawal
	Visit	Home	Home	Home	Home/ Telephone	Home	Home	Visit	Visit
Informed consent	X								
Inclusion/exclusion	X								
Medical history (including previous use of NSAIDs for sciatica)	X								
Treatment of current sciatica episode	X								
Physical examination*	X								
Vital signs (blood pressure, pulse)	X							X	X
Questionnaires:									
Leg pain intensity, back pain intensity	X, X†	X	X	X	X	X	X	X	X
Questionnaires:									
SBI, RMDQ-S	X				X		X	X	X

	Baseline	Start of treatment			Halfway follow-up		End of treatment	Final study visit	Withdrawal
Day	0	1	2	3-4	5 ( $\pm 1$ )	6-9	10	12 ( $\pm 2$ )	within 7 days after withdrawal
Questionnaire: GPC					X		X	X	X
Questionnaire: Work/study	X						X	X	X
Patient's guess regarding correct treatment								X	X
Self-report of IMD and rescue medication intake		X	X	X	X	X	X		
Protocol compliance, patient discontinuation			X		X			X	
Adverse events, self-report		X	X	X	X	X	X		
Adverse events, investigator					X			X	X
Laboratory tests† (safety)	X							X	X
Pregnancy test (women of childbearing potential)	X								
Return of pill boxes								X	X

\*SLR, sensory, muscular strength and reflex status of the lower extremities

†On day 0 patients will record back and leg pain both at the clinic and at home in the evening

‡Haemoglobin, hematocrit, leucocytes, thrombocytes, creatinin/eGFR, ASAT, ALAT, ALP

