### **7.1.2 Non-serious AEs**

Since the AE profile of Naproxen is well established, non-serious AEs will be recorded, but not reported to the Norwegian Medicines Agency. The same goes for Paracetamol. The eCRF will include a daily checklist including expected non-serious AEs (see section 7.2) as well as space to specify other unpleasant events.

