## **7.4 RECORDING OF ADVERSE EVENTS**

### **7.4.1 Non-serious AEs**

Patients may record non-serious AEs on a tick off list including 10 events expected for Naproxen, see section 7.2.1. Additionally, patients may report other non-serious AEs in their own words. At the follow-up at 5 ( $\pm 1$ ) at the final study visit the investigator will record whether the event is resolved or still ongoing and whether any action was taken.

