### **7.4.2 Serious AE**

The investigator will record the following information in the CRF:

The nature of the event(s) will be described by the investigator in precise standard medical terminology (i.e. not necessarily the exact words used by the patient).

The duration of the event will be described in terms of event onset date and event ended date.

The intensity of the adverse event will be classified as Mild / Moderate / Severe; according to Common Terminology Criteria for Adverse Events version 4.0 (CTCAE).

The Causal relationship of the event to the study medication will be assessed as one of the following:

- Unrelated. There is not a temporal relationship to investigational product administration (too early, or late, or investigational product not taken), or there is a reasonable causal relationship between non-investigational product, concurrent disease, or circumstance and the AE.
- Unlikely. There is a temporal relationship to investigational product administration, but there is not a reasonable causal relationship between the investigational product and the AE.
- Possible. There is reasonable causal relationship between the investigational product and the AE. Dechallenge information is lacking or unclear.
- Probable. There is a reasonable causal relationship between the investigational product and the AE. The event responds to dechallenge. Rechallenge is not required.
- Definite. There is a reasonable causal relationship between the investigational product and the AE.

Action taken: The outcome of the adverse event – whether the event is resolved or still ongoing.

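### The adverse event tick list has no pre-dose entry, so symptoms first ticked on day 1 cannot be shown to be new, and the comparison of non-serious adverse events is probably diluted.

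*SAP*

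**What the plan says.** - **Definition (SAP 30).** "An adverse event is an untoward medical occurrence after the administration of the first dose of a study drug"; the window closes at the final visit, scheduled for day 12 (±2). Event counts and the share of subjects with one or more are summarised by arm and severity, and tested by chi-square.
- **Instrument (Protocol 7.1.2, 7.2.1, 7.4.1).** "The eCRF will include a daily checklist including expected non-serious AEs", with space for other events. The ten items are dyspepsia, nausea, diarrhoea, vomiting, abdominal pain, skin eruption, tinnitus, headache, tiredness and dizziness.
- **Schedule (Protocol 6.1).** The row "Adverse events, self-report" is marked for days 1 to 10. The row "Adverse events, investigator" is marked for day 5, the final visit and the withdrawal visit. Neither is marked at day 0.
- **Non-serious events (Protocol 7.4.1).** At day 5 and the final visit, "the investigator will record whether the event is resolved or still ongoing and whether any action was taken". Neither onset nor change from baseline is listed.
- **Serious events (Protocol 7.4.2).** "The duration of the event will be described in terms of event onset date and event ended date".
- **Before dosing.** Baseline takes medical history and concomitant medication (Protocol 6.2.3). There is no specific washout, and study medication starts the morning after inclusion (6.2.2). Patients already make a home diary entry on the evening of day 0, but only for leg and back pain (footnote to the flow chart).

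Neither document states a treatment-emergent or new-or-worsened rule.

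**The concern.** The listed symptoms are common, and several could be present before the first capsule. Patients enter with leg pain of at least 4 out of 10. Protocol 1.2.1 cites cohorts in which 50-60% were taking an NSAID at baseline, so some may arrive with symptoms from earlier use of the same drug class. A headache carried over from day 0 and one that began after the first dose give the same day-1 tick.

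If carried-over symptoms are counted, they enter both arms. Randomisation balances them, so no false difference is expected, but a real one shrinks. Protocol 1.6 says that a positive trial should let clinicians and patients weigh benefit against adverse events. For safety, dilution errs in the unhelpful direction: naproxen would look better tolerated than it is.

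**Working it through.** **The plan's own figure.** The documents give no calculation for adverse events. The efficacy sample size supplies the number per arm. A difference of 1.5 with SD 2.5, two-sided 5% and 90% power gives 59 per arm by the normal formula and 59.35 by the t test, so 60. Then 120 / (1 − 0.20) = 150, or 75 per arm. This agrees with Protocol 9.1 and SAP 11, and the present point does not affect it.

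**Which ticks are ambiguous.** The list is daily, and SAP 15 opens each form only on its scheduled date, so each symptom has a dated first tick.
- First tick on day 2 or later: the symptom was not reported on day 1 and can be dated after dosing, unless it comes and goes.
- First tick on day 1: it may precede or follow the first dose, and no planned item separates the two.

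**Dilution.** Let b be the share with a listed symptom before dosing, t the share of those who tick it after dosing, and p the new-onset rate. With c = b × t equal in both arms and independent of new onset:

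observed rate = c + (1 − c)p

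observed difference = (1 − c) × true difference

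**Power.** With d the observed difference, p̄ the mean of the two observed rates and n = 75:

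power = Φ[(d − 1.96 × se0) / se1], where se0 = √(2p̄(1 − p̄)/n) and se1 = √((p1(1 − p1) + p2(1 − p2))/n)

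**Assumptions.** New-onset rates are 25% on placebo and 45% on naproxen. The documents give no placebo rate and no pre-dose prevalence, so b is shown as a range.

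Example, b = 20%, t = 1: rates are 0.20 + 0.80 × 0.25 = 40% and 0.20 + 0.80 × 0.45 = 56%; d = 0.16, se0 = 0.0816, se1 = 0.0805; power = 50%.

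| b | observed, all tick (t = 1) | difference, points | power, all tick | power, half tick (t = 0.5) |
|---|---|---|---|---|
| 0% | 25 v 45% | 20 | 73% | 73% |
| 20% | 40 v 56% | 16 | 50% | 61% |
| 40% | 55 v 67% | 12 | 32% | 50% |
| 60% | 70 v 78% | 8 | 20% | 40% |

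**What a day-0 record recovers.** Limiting the comparison to patients free of listed symptoms at day 0 leaves 75(1 − b) per arm, that is 60, 45 and 30, and keeps the 20-point difference. Power is then 63%, 51% and 37% for b = 20%, 40% and 60%, against 50%, 32% and 20% when all tick.

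**One symptom.** Protocol 1.5.3 gives dyspepsia as 14%. Against an assumed 5% on placebo, power is 47% with b = 0. With b = 20% and t = 1 the observed rates are 31.2% v 24.0%; power is 16% without the record and 39% with it (60 per arm).

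**Type I error.** With equal new-onset rates the observed rates are equal too. A simulation at 20% in both arms and b = 30% rejected in 5.7% of runs, close to the nominal 5%.

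**The case against.** The strongest case on the other side has five parts.

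1. **The definition already excludes pre-existing symptoms.** As a statement of intent, yes, and a reader should not infer that the SAP means to count them. But for day-1 ticks the planned data cannot apply it.
2. **The diary dates events.** This stands. A reader might infer that nothing in the schedule separates old symptoms from new. The documents do not support that: first ticks from day 2 onward are datable, investigators ask about events twice, and a medical history is taken. What remains is day-1 ticks and intermittent symptoms, since the history is not matched to the ten items and no rule uses it.
3. **The eCRF wording is not shown.** It may ask only about new symptoms. SAP 30 and Table 7 plan severity, which Protocol 7.4.1 does not list, so 7.4.1 may not be a full account of the form. This stands as a limit on certainty.
4. **Carry-over may not be equal.** Symptoms from earlier NSAID use could fade on placebo and persist on naproxen. They would then not simply add equally to both arms, and a strict new-or-worsened count would hide a real difference. This stands, and the fix allows for it.
5. **The trial is sized for leg pain.** There is no safety hypothesis or power claim, serious events carry onset dates, and discontinuations for treatment-related events are reported separately. This limits the importance of the point but does not remove it, because the chi-square comparison is planned.

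**Conclusion.** The gap is real but limited. With no pre-dose list and no recorded comparison with baseline, the after-first-dose definition cannot be applied to non-serious symptoms first ticked on day 1, or to intermittent ones. Under equal carry-over the planned comparison is pulled towards no difference, by a factor equal to one minus the share of patients who tick a carried-over symptom. The size cannot be fixed from the documents: the power figures rest on assumed new-onset rates, an assumed prevalence range, 75 analysed per arm and equal persistence in both arms.

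A reader might go further and conclude that the safety analysis is invalid or that it can produce a false harm signal. Neither follows. The type I error stays near 5%, serious events are dated, and the primary efficacy analysis is untouched. This is a worthwhile, inexpensive improvement to the summary of non-serious events.

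**What to change.** - **Flow chart and diary.** Add the same ten items and the free-text field to the existing day-0 evening entry, and mark day 0 in the self-report row.
- **SAP 30 and Table 7.** Report day-0 prevalence by arm. Count a listed symptom as treatment-emergent if it was absent on day 0 or has worsened since. Keep the summary of all ticks alongside, so that symptoms persisting in one arm and resolving in the other stay visible.
- **Investigator record.** Add a worsening field to the day-5 and final-visit adverse event record; Protocol 7.4.1 lists none.
- **Patients already treated.** First enrolment was planned for September 2017 and the SAP cites sources accessed in 2021, so a day-0 list may be out of reach for some or all patients. For them, add a sensitivity analysis that excludes symptoms first ticked on day 1, and state the limitation. It also drops genuine first-day events, so it should sit beside the main count and not replace it.

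The cost is about a minute of patient time on day 0, one extra CRF field with a brief assessment at contacts already scheduled, and a few sentences in the SAP. Some symptoms that began before dosing leave the treatment-emergent count, which is why the all-ticks summary is kept.

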32.1 Planned tables

- Table 1. Baseline characteristics of participants by treatment group
- Table 2. Intervention effect on primary and secondary outcomes
- Table 3. Important and not important protocol deviations by treatment group
- Table 4. Baseline concomitant medications by treatment group
- Table 5. Response to blinding question at day 10
- Table 6. Global perceived change (including all response categories) at day 5 and day 10 by treatment group
- Table 7. Adverse events by treatment group and severity (mild / moderate / severe)
- Table 8. Results of sensitivity analyses

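### The SAP splits all adverse events by severity, but the protocol specifies a severity grade only for serious events

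*SAP*

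**What the plan says.** **What the analysis asks for.** SAP section 30 covers "The number of non-serious and serious adverse events, and the proportion of subjects reporting" one or more events, and says that these "will be summarized by treatment group and severity (mild / moderate / severe". The list of planned tables in SAP 32.1 has the same split: "Table 7. Adverse events by treatment group and severity (mild / moderate / severe". Neither place limits it to serious events, and section 30 names both kinds.

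**What the protocol collects for non-serious events.** Section 7.1.2 says: "The eCRF will include a daily checklist including expected non-serious AEs", with space for other events. Section 7.4.1 adds: "Patients may record non-serious AEs on a tick off list including 10 events expected for Naproxen", and "Additionally, patients may report other non-serious AEs in their own words". At the day 5 follow-up and the final visit, "the investigator will record whether the event is resolved or still ongoing and whether any action was taken". No intensity item appears in either section.

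**What the protocol collects for serious events.** Section 7.4.2, headed Serious AE, lists nature, duration, intensity, causality and outcome. On intensity it says: "The intensity of the adverse event will be classified as Mild / Moderate / Severe", using CTCAE version 4.0.

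**The concern.** Severity and seriousness are different attributes. A non-serious dyspepsia can be mild or severe, and a tick on a list does not say which. The SAP needs a grade for every event, while the protocol sets one up for serious events only. If the trial collects what the protocol describes, the severity breakdown is empty for the events that patients report every day.

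Two consequences follow. First, a grade that was not recorded at the time cannot be soundly recovered later from a tick or a line of free text, and the SAP gives no rule for doing so and names no grader. Second, SAP section 32 bases summaries on patients with non-missing values and shows only the categories in which someone had a response. Ungraded events could then disappear from Table 7 without a visible row for missing severity.

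Protocol section 1.6 says that, if naproxen works, the results should allow its benefit to be weighed against its adverse events. Table 7 is the main planned table for the second half of that comparison.

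**Working it through.** The plan gives no figure on this point to reproduce. The check compares the data the SAP needs with the data the protocol specifies.

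| Item | Non-serious events | Serious events |
|---|---|---|
| First record | Patient: daily tick list and free text (Protocol 7.1.2, 7.4.1) | Investigator, in the CRF (Protocol 7.4.2) |
| Investigator adds | Current status and action taken (7.4.1) | Nature, duration, intensity, causality, outcome (7.4.2) |
| Severity grade specified | None | Mild/moderate/severe, CTCAE v4.0 (7.4.2) |
| Severity grade needed by SAP 30 and Table 7 | Yes | Yes |

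**Step 1: is the grade specified elsewhere?** The flow chart in protocol section 6.1 has two adverse event rows, one for patient self-report on days 1 to 10 and one for the investigator at day 5, the final visit and withdrawal. Neither mentions severity. SAP section 30 uses the grade but does not say where it comes from.

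**Step 2: could 7.4.2 be meant for all events?** Its intensity sentence speaks of the adverse event in general. But the section is headed Serious AE and follows a separate section that gives non-serious events their own list of recorded items. Protocol 8.2 likewise mentions causality assessment in the source records only for serious events. The natural reading is that the fuller assessment is for serious events.

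**Step 3: how many events might be affected?** The documents give no serious-event rate, so the share of Table 7 without a specified grade cannot be calculated. For scale only, take two rates from protocol 1.5.3, headache 15% and dyspepsia 14%. Both events are on the tick list in 7.2.1. With 150 patients allocated 1:1, the naproxen arm has 150 / 2 = 75.

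- Headache: 75 × 0.15 = 11.25, about 11 patients.
- Dyspepsia: 75 × 0.14 = 10.5, about 10 to 11 patients.
- At half those rates: 75 × 0.075 = 5.6 and 75 × 0.07 = 5.25, about 5 to 6 and about 5 patients.

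This assumes that the rates are proportions of patients and that they carry over to 10 days in this population, which the documents do not show. Even at half the rates, two event types alone would give several naproxen patients an event for which the protocol specifies no grade.

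**The case against.** The strongest reply is that tables are built from eCRF fields, not from protocol prose. SAP 33.3 lists the eCRF among the documents reviewed when the SAP was written, so its authors may have specified the split because the field exists. The flow chart confirms that investigators make their own adverse event entry, and 7.4.1 does not say that its list is exhaustive. This stands as a limit. A reader might infer that Table 7 cannot be produced, but without the eCRF the documents show only that the protocol names no source for the grade. A field would not fully settle the matter either, because the documents would still not say who grades non-serious events, when, or on what scale.

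A reader might also infer that virtually every entry in Table 7 would lack a grade. The documents do not support a figure. The ten expected events in 7.2.1 are all non-serious because that is what the list is defined to contain. That most events will be non-serious is a reasonable expectation over 10 days, with high-risk patients excluded, but it remains an expectation.

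A third inference would be that treatment-related discontinuations in SAP section 30 are equally unsupported. They are not: the same sentence assigns that judgement to the principal investigator, and protocol 6.3 and 8.2 require the reason for discontinuation to be recorded.

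Finally, the loss is limited. Without grades, section 30 still provides event counts by seriousness, the proportion of patients with at least one event, and discontinuations, all by arm. No efficacy result is affected. This is fair, and it is why the matter is a safety-reporting gap and not a threat to the trial's main conclusion.

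**Conclusion.** The mismatch holds. SAP section 30 and Table 7 require a severity grade for all adverse events, and the protocol specifies one for serious events only. For non-serious events the severity split has no specified data source, and SAP section 32 could let ungraded events fall out of the table unseen.

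The size is one stratifier of one planned safety table, probably for most of the events in it. That rests on two assumptions: that non-serious events predominate, for which no rate is documented, and that the eCRF holds no severity field for them, which cannot be checked here. If the field exists, what remains is a wording gap about grader, timing and scale. The point should be settled before database lock, since a missing grade cannot be repaired at analysis.

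**What to change.** First check whether the eCRF already records severity for non-serious events. If it does, state in protocol 7.4.1 and SAP section 30 who assigns the grade, when and on what scale.

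If it does not, add a mild/moderate/severe grade to the investigator's adverse event review at day 5, the final visit and withdrawal, and name the scale in 7.4.1. The contacts already exist, so the cost is one extra field and possibly an amendment under protocol 10.3. A new field does not grade events already collected. First enrolment was planned for September 2017 and the SAP's references show access dates in 2021, so many events may predate the change. Report those as ungraded, in a visible row.

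If enrolment is too far advanced, restrict the severity breakdown in SAP section 30 and Table 7 to serious events. Tabulate non-serious events by type and treatment group, giving the number of events and of patients with at least one, and do no retrospective grading. This needs only a change of SAP wording, and it gives up severity information on non-serious events.

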## LIST OF ABBREVIATIONS AND DEFINITIONS OF TERMS

Abbreviation or special term	Explanation
AE	Adverse Event
COX	Cyclooxygenase
CT	Computed tomography
DAE	Discontinuation due to Adverse Event
DDD	Defined Daily Dose
eCRF	Electronic Case Report Form
GCP	Good Clinical Practice
GI	Gastrointestinal
GPC	Global perceived change
IB	Investigator's Brochure
ICF	Informed Consent Form
ICH	International Conference on Harmonisation
IMP	Investigational Medicinal Product (includes active comparator and placebo)
MRI	Magnetic resonance imaging
NNT	Number Needed to Treat
NRS	Numeric rating scale
NSAID	Non-steroidal anti-inflammatory drug
OTC	Over-the-counter
PRO	Patient Reported Outcome
RCT	Randomized Controlled Trial
REK	The Norwegian Regional Ethics Committee South East
RMDQ-S	Roland Morris Disability Questionnaire modified for use in sciatica
SAE	Serious Adverse Event
SBI	Sciatica Bothersomeness Index
SPC	Summary of Product Characteristics
SLR	Straight leg raising

ULN	Upper limit of normal
-----	-----------------------

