## 6.3 CRITERIA FOR PATIENT DISCONTINUATION

Patients may be discontinued from study treatment and assessments at any time. The reason for discontinuation will be recorded. Specific reasons for discontinuing a patient for this study are:

- Voluntary discontinuation by the patient
- Safety reason as judged by the Principal Investigator
- Major protocol deviation
- Incorrect enrolment ie, the patient does not meet the required inclusion/exclusion criteria for the study
- Patient lost to follow-up
- A female patient becoming pregnant
- Patient's non-compliance to study treatment and/or procedures

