## 6.4 PROCEDURES FOR DISCONTINUATION

### 6.4.1 Patient Discontinuation

The patient is not obliged to give his or her reasons for withdrawing prematurely from the trial. However, a reasonable effort will be made to ascertain the reason, while fully respecting the patient's rights. If he or she is unwilling or unable to complete of the final study visit he or she will be invited to report safety and efficacy endpoints either in the eCRF or by phone. Special consideration will be given to collect remaining medication and pill boxes. If the withdrawal is exclusively related to the trial drug therapy, this will be classified as a violation of the protocol and the data collection will be continued as specified in 6.2.4 and 6.2.5. Patient discontinuation will be monitored by checking the eCRF at day 2 and at the telephone follow-up at day 5 ( $\pm 1$ ).

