Amendment: Subjects who are withdrawn because they did not receive the study medication may be re-randomized. This requires that the reason for not receiving the study medication was unrelated to the subject's condition and that all eligibility criteria are met. In such cases the subject ID linked to the first randomization will be excluded from all analyses. The subject concerned will be analyzed according to the second randomization and included in the appropriate analysis populations.

TRIAL POPULATION

21 Screening data

The population of interest is patients with severe sciatica who are referred to the participating centers, i.e. outpatient pain/back clinics at public hospitals in Norway. To enhance recruitment primary care clinicians are invited to refer eligible patients. A prescreening log will be established including information about age, sex and whether the eligibility criteria were fulfilled. Reasons why eligible subjects were not enrolled will be noted.

22 Eligibility

See trial protocol for inclusion and exclusion criteria.

23 Recruitment

We will present a CONSORT [2] diagram comprising the number of participants who were screened, eligible, randomized, receiving their allocated treatment, withdrawn and lost to follow-up.

24 Withdrawal and loss to follow-up

Reasons for withdrawal from the study will be coded as follows:

- Voluntary discontinuation by the patient
- Safety reason as judged by the principal investigator
- Important (major) protocol deviations
- Incorrect enrolment i.e. the patient does not meet the required inclusion/exclusion criteria for the study
- Patient lost to follow-up
- A female patient becoming pregnant
- Patient's non-compliance to study treatment and/or procedures
- Death
- Other

Reasons for loss to follow-up will be provided if known. Depending on the data we will present the timing of withdrawal and loss to follow up in a Kaplan-Meier graph or incorporate it into the CONSORT flow diagram.

25 Baseline patient characteristics

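### SAP 30 counts treatment discontinuations only when the adverse event is judged treatment-related; no count by arm of stopping study medication for any adverse event is planned

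*SAP*

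**What the plan says.** **The planned result.** SAP 30 summarises all adverse events by arm and severity with no causality filter. For discontinuation it narrows to the number and "reasons for treatment discontinuation because of a treatment-related adverse event, as judged by the principal investigator".

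**Causality.** Protocol 7.4.2, headed Serious AE, gives a five-category scale: "The Causal relationship of the event to the study medication will be assessed as one of the following". Protocol 7.4.1, on non-serious events, asks the investigator only whether the event has resolved and whether action was taken.

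**Reason codes.** SAP 24 has nine codes and introduces them with "Reasons for withdrawal from the study will be coded as follows". None is labelled adverse event. The nearest is "Safety reason as judged by the principal investigator", and there are also voluntary, non-compliance and other codes. Protocol 6.3 carries the same safety entry, in a list of criteria that covers study treatment and assessments together ("Patients may be discontinued from study treatment and assessments at any time").

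**Stopping the drug but staying in the trial.** Protocol 6.4.1 states: "If the withdrawal is exclusively related to the trial drug therapy, this will be classified as a violation of the protocol". Data collection then continues.

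**Reasons collected whatever the cause.** Protocol 8.2 requires the medical record to hold the date of and reason for stopping study treatment, separately from those for leaving the study. Under SAP 19.1 patients give a daily reason for any dose not taken as prescribed, and reasons for non-adherence are to be reported. Lists 3 and 4 in SAP 32.2 present reasons for non-adherence and for withdrawal.

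**The concern.** Protocol 1.6 says that, if naproxen proves effective, the results should let clinicians and patients weigh benefit against adverse events. How many patients stopped the capsules because of an adverse event is a natural part of that account over ten days of treatment.

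The planned count passes through a judgement of relatedness. For the commonest candidates (Protocol 7.2.1 lists dyspepsia, nausea, abdominal pain and others as expected non-serious events) the protocol specifies no scale or field on which that judgement would be recorded. A patient who decides to stop because of dyspepsia may or may not be counted, and the plan gives no rule for deciding. No unfiltered count by arm is planned to set beside it.

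**Working it through.** The plan states no figure on this point, so there is none to reproduce. The check sets the sections side by side; an illustration on assumed rates follows.

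**Step 1. Direction.** Let D be the number in an arm who stop study medication with an adverse event as a reason, and s the share of those judged treatment-related. SAP 30 reports R = s × D. Since s lies between 0 and 1, R ≤ D, with equality only when s = 1.

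**Step 2. Is s defined?** For serious events, yes (Protocol 7.4.2). For non-serious events, Protocol 7.4.1 specifies no causality item. The eCRF is not among the documents, so it may hold such a field, but neither protocol nor SAP specifies one.

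**Step 3. Could D be read from another planned output?**

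| Planned output | What it gives | Does it give D by arm? |
|---|---|---|
| Table 7 | Adverse events by arm and severity | No link to stopping |
| Table 3 | Important and minor deviations by arm, including adherence below 80% | No reason given; late stops missed |
| Figures 3 and 4 | Study medication use and adherence by arm | No reason given |
| List 3 | Reasons for non-adherence | A listing; its title does not mention arm |
| List 4 | Reasons for withdrawal from the study | Does not cover stopping the drug alone |

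On Table 3, the full course is 20 doses (SAP 19.1), and 80% × 20 = 16. A patient who takes every dose through day 8 has taken 8 × 2 = 16, exactly 80%, so stopping after that does not meet the below-80% criterion.

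**Step 4. Illustration on assumed rates.** The plan's 150 patients at 1:1 give 75 per arm. If s is the same in both arms, the reported risk difference is s × (pN − pP), where pN and pP are the true proportions stopping for any adverse event on naproxen and placebo. These rates and shares are assumptions; none comes from the documents.

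| Assumed pN v pP | s = 1 | s = 0.75 | s = 0.50 | s = 0.25 |
|---|---|---|---|---|
| 5% v 2% | 3.0 points | 2.3 | 1.5 | 0.8 |
| 10% v 4% | 6.0 points | 4.5 | 3.0 | 1.5 |
| 15% v 5% | 10.0 points | 7.5 | 5.0 | 2.5 |

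In the middle row the expected counts are 75 × 0.10 = 7.5 against 75 × 0.04 = 3.0 when s = 1, and 3.8 against 1.5 when s = 0.50. The ratio stays at 2.5 throughout because s cancels; only the absolute difference shrinks.

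**The case against.** The strongest reply is that little is hidden. All adverse events are reported by arm without a causality filter, reasons for non-adherence and withdrawal are listed whatever their cause, and investigators are blinded (Protocol 9.2.2), so the judgement need not favour either arm. What is missing is one cross-tabulation. All of that is correct, and it limits the weight of the point. It does not remove it, because none of those outputs gives the number by arm.

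A reader might also infer four stronger things that the documents do not support.

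- **That stopping for intolerance will be under-counted.** This is a risk. If every case is judged related, s = 1 and nothing is lost.
- **That no code exists for such a stop.** Only the label is absent. The lists have a safety code ("Safety reason as judged by the Principal Investigator" in Protocol 6.3), and SAP 24 also has an other category. The safety code does rest on the principal investigator's judgement, so a patient's own decision to stop could be coded elsewhere.
- **That miscoding under SAP 24 lowers the SAP 30 count.** SAP 24 concerns leaving the study, and nothing says that its codes feed SAP 30.
- **That a commitment has been broken.** The protocol's abbreviation list includes "Discontinuation due to Adverse Event", but the term is not used again in the protocol or SAP text, and an unused abbreviation promises no analysis.

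**Conclusion.** The point holds as a reporting gap. SAP 30 restricts its discontinuation result to events judged treatment-related, the documents specify no causality assessment for non-serious events, and no unfiltered count by arm is planned. The reported number is therefore at most the number who stopped for any adverse event. By how much it falls short cannot be determined from the documents, and the tables above show only how the loss would scale if the share judged related were equal across arms. A bias between arms is not shown: the judgement is blinded, although recognisable drug effects could influence it.

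Two limits apply. The eCRF was not available, so a causality field for non-serious events may exist there. And Protocol 6.4.1 does not oblige patients to explain a withdrawal, so an unfiltered count will be only as complete as the reasons given.

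The change is worth making because it is specific, improves the harm summary and costs little. It does not affect the primary analysis.

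**What to change.** **SAP 30.** Report by arm the number and percentage of patients who permanently stopped study medication with an adverse event recorded as a reason, regardless of judged causality and of who took the decision. Keep the treatment-related count as a sub-row, and state how relatedness is judged for non-serious events.

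**Source.** Derive the count from the recorded reason for discontinuing study treatment (Protocol 8.2) and the daily diary reasons (SAP 19.1), coded before the A/B treatment codes are attached to the data.

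**SAP 24.** Add an adverse event category to the reporting codes, and tabulate it separately for stopping study medication and for leaving the study.

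**Leave Protocol 6.3 unchanged.** It sets criteria for discontinuing patients, and this point concerns only how discontinuations are reported.

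**Cost.** SAP wording and a small amount of blinded coding of text already collected. No new assessments are needed, and sample size, power and significance level do not change.
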